5.8 Duration of Follow Up

Participants will be followed on-study until death. Participants removed from protocol therapy for unacceptable adverse event(s) will be followed until resolution or stabilization of the adverse event. An additional adverse event assessment will be performed 90 days (-15/+30 days) after the last dose of treatment for participants who receive pembrolizumab, including participants who stopped early for CR, are candidates for retreatment, and have not yet restarted pembrolizumab. This may be conducted by phone.

Participants who discontinued therapy for reasons other than progression will be followed for first disease progression or until the start of another anti-cancer therapy. Tumor assessments should continue to be performed every 9-12 weeks on these participants until first disease progression event, start of another anti-cancer therapy, or death, whichever occurs first. Research bloods are optional at the time of tumor assessments. At either the time of disease progression or start of another anti-cancer therapy, participants will then be followed for survival.

Participants will be followed or contacted every 6 months for survival.

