7.2 Adverse Event Characteristics

- **CTCAE term (AE description) and grade:** The descriptions and grading scales found in the revised NCI Common Terminology Criteria for Adverse Events (CTCAE) version 5.0 will be utilized for AE reporting. All appropriate treatment areas should have access to a copy of the CTCAE version 5.0. A copy of the CTCAE version 5.0 can be downloaded from the CTEP web site
http://ctep.cancer.gov/protocolDevelopment/electronic_applications/ctc.htm.
- **For expedited reporting purposes only:**
 - AEs for the agent(s) that are listed above should be reported only if the adverse event varies in nature, intensity or frequency from the expected toxicity information which is provided.
- **Attribution of the AE:**
 - Definite – The AE is *clearly related* to the study treatment.
 - Probable – The AE is *likely related* to the study treatment.
 - Possible – The AE *may be related* to the study treatment.
 - Unlikely – The AE is *doubtfully related* to the study treatment.
 - Unrelated – The AE is *clearly NOT related* to the study treatment.
- **Expectedness of the AE:**
Adverse events can be ‘Expected’ or ‘Unexpected’
 - Expected adverse event

Expected adverse events are those that have been previously identified as resulting from administration of the agent. For the purposes of this study, an adverse event is considered expected when it appears in the current adverse event list, the Investigator's Brochure, the package insert or is included in the informed consent document as a potential risk.

- Unexpected adverse event

For the purposes of this study, an adverse event is considered unexpected

when it varies in nature, intensity or frequency from information provided in the current adverse event list, the Investigator's Brochure, the package insert or when it is not included in the informed consent document as a potential risk.

Investigators **must** report to the Sponsor-Investigator any serious adverse event (SAE) that occurs after the initial dose of study treatment, during treatment, or within 30 days of the last dose of treatment on the local institutional SAE form (90 days for pembrolizumab).

In the event of an unanticipated problem or life-threatening complications treating investigators must immediately notify the Sponsor-Investigator.

All occurrences of potential DILIs, meeting the defined criteria in Section 5.5, must be reported as SAEs.

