7.6 Expedited Reporting to [REDACTED]

A serious adverse event is any adverse event occurring at any dose or during any use of [REDACTED] product (i.e., Arm A only) that:

- Results in death;
- Is life threatening;
- Results in persistent or significant disability/incapacity;
- Results in or prolongs an existing inpatient hospitalization;
- Is a congenital anomaly/birth defect;
- Is a new cancer (that is not a condition of the study);
- Is associated with an overdose;
- Is another important medical event

Any serious adverse event, or follow up to a serious adverse event, including death due to any cause other than progression of the cancer under study that occurs to any subject from the time the consent is signed through 90 days following cessation of pembrolizumab, or the initiation of new anti-cancer therapy, whichever is earlier, whether or not related to [REDACTED] product, must be reported within 24 hours to the Sponsor-Investigator and within 2 working days to [REDACTED] [REDACTED] on a MedWatch 3500A Form.

Non-serious Events of Clinical Interest will be forwarded to [REDACTED] and will be handled in the same manner as SAEs. Medwatch 3500A Forms will be used for these reports.

Additionally, any serious adverse event, considered by an investigator who is a qualified physician to be related to [REDACTED] product that is brought to the attention of the investigator at any time outside of the time period specified in the previous paragraph also must be reported immediately to [REDACTED]

SAE reports and any other relevant safety information are to be forwarded to the [REDACTED]

Any SAE that is reportable to the FDA should also be transmitted to [REDACTED] at the

number above.

All subjects with serious adverse events must be followed up for outcome.

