7.7 Expedited Reporting to [REDACTED]

A serious adverse event is any adverse event occurring at any dose or during any use of [REDACTED] product that:

- Results in death;
- Is life-threatening;
- Results in persistent or significant disability/incapacity;
- Results in or prolongs an existing inpatient hospitalization;
- Is a congenital anomaly/birth defect;

- Is a new cancer (that is not a condition of the study);
- Is associated with an overdose;
- Is another important medical event

All SAEs and pregnancies must be reported to the Sponsor-Investigator within 24 hours of awareness of the event. These events should be reported to [REDACTED] within 15 working days of event awareness.

The initial SAE report should be as complete as possible; however, reporting should not be delayed in order to obtain more information. Follow-ups should be reported as appropriate. The study team is required to provide follow-up information in response to queries from [REDACTED] or their designee.

All SAEs from the time the subject signs the informed consent and until 30 days after the last dose of study drug must be reported. During the period after informed consent has been obtained and before the first dose of study drug has been administered, only SAEs caused by a protocol-mandated intervention (e.g., biopsy) should be reported. Any SAE that occurs 30 days after the last dose of study drug and is assessed as possibly related to study drug must be reported.

All SAEs from the time the subject signs the informed consent and until 30 days after the last dose of study drug must be reported. During the period after informed consent has been obtained and before the first dose of study drug has been administered, only SAEs caused by a protocol-mandated intervention (e.g., biopsy) should be reported. Any SAE that occurs 30 days after the last dose of study drug and is assessed as possibly related to study drug must be reported.

All SAEs and Pregnancies/Exposure During Pregnancies should be reported via email to:
[REDACTED]

Case Type	Timeframe	Format	Method
Serious Adverse Event	15 working days of awareness	Medwatch 3500A	email to [REDACTED]
Pregnancy/Exposure During Pregnancy	15 working days of awareness	Medwatch 3500A	email to [REDACTED]

Any SAE that meets FDA reporting criteria will also be reported to [REDACTED] as per above.

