- m. End of treatment (EOT) visit is to occur within 45 days of final administration of study treatment, at the time of the subsequent visit that follows progression/other off treatment reason. If the EOT visit occurs within 30 days of final study treatment, an additional AE assessment is performed 30-45 days from final administration of study treatment; this may be conducted in person or by phone by the investigator or suitably trained and qualified delegate (e.g. MD, RN, NP, etc.).
- n. For those stopping treatment for reasons other than progressive disease (i.e., complete response), tumor measurements should continue to be repeated every 9-12 weeks until initiation of retreatment on this study, another anti-cancer therapy, progression, or death, whichever occurs first.
- o. Samples during follow up should be drawn every 9-12 weeks, alongside tumor assessments, for patients who come off treatment for reasons other than progressive disease until the initiation of another anti-cancer therapy, progression, or death, whichever occurs first.

- p. An adverse event assessment is performed 90 days (-15/+30 days) after the last dose of pembrolizumab (Arm A patients only). This may be conducted in person or by phone by the investigator or suitably trained and qualified delegate (e.g., MD, RN, NP, etc.).
- q. Patient reported outcomes per Section 9.9 should be performed during screening or on C1D1 prior to treatment (baseline), at the clinic visit following a restaging scan, and at end of treatment/progressive disease.
- r. For subjects on Arm A, if sacituzumab govitecan is discontinued and pembrolizumab is continued, Day 8 assessments (AE assessment, labs, vitals, etc.) are not needed.

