13.6 Analysis of Secondary Endpoints

Efficacy Endpoints

- Among patients who initiated protocol therapy and whose tumor was centrally confirmed to be PD-L1-positive (as defined by CPS ≥ 1 using the PharmDx 22C3 assay), the efficacy, as assessed by PFS, of sacituzumab govitecan plus pembrolizumab will be compared to sacituzumab govitecan alone. PD-L1 status will be defined by central confirmation of PD-L1 testing on the baseline research biopsy, if available; if not available, then the central PD-L1 testing results from the archival sample will be used. The comparison of PFS between treatment arms in the PD-L1-positive subgroup will be exploratory.
- In the modified ITT and PD-L1-positive population, all patients who initiated protocol therapy will also be evaluated for ORR (according to RECIST 1.1), CBR, DOR, TTOR and OS.

Radiographic response will be assessed using RECIST 1.1 criteria, as defined in section 11. Objective response will require confirmatory scans or exam as indicated. The ORR (CR + PR), according to RECIST 1.1, will be reported with 95% confidence intervals. Clinical benefit is defined as CR, PR or SD ≥ 24 weeks according to RECIST 1.1 and will be reported with 95% confidence intervals. Median DOR and TTOR will be reported with ranges. Overall survival, defined as the time from randomization (or registration) to death due to any cause with censoring at date last known alive, will be reported with Kaplan Meier estimates.

For OS, the log-rank test will be one-sided. Treatment efficacy in these secondary endpoints will be assessed by Cox models adjusting for clinical factors such as age at study entry, stage (locally advanced or metastatic), visceral metastases (yes or no), level of ER expression (1-9% vs. 10% or greater), and rapid recurrence after completion of adjuvant therapy < 6 months (yes or no). Dichotomous endpoints of response will be compared using Cochran-Maentel-Haenszel chi-squared tests.

Safety and tolerability

All patients will be evaluable for toxicity from the time of their first treatment with any study agent. Toxicity will be graded according to NCI CTCAE, Version 5.0. Toxicities will be summarized by maximum grade and by treatment arm. Incidence rate of each toxicity will be reported with 95% confidence intervals. The incidence rates of any grade 3 or higher toxicity will be compared across arms using a two-sided Fisher's exact test.

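### The Grade 3+ toxicity comparison in Section 13.6 has no common cut-off, although adverse events are followed to about 90 days in Arm A and only 30-45 days in Arm B

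*Combined protocol and SAP*

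**What the plan says.** **Both arms.** Footnote m of the Study Calendar (Section 10) places the end-of-treatment visit within 45 days of the final dose. If that visit falls within 30 days, "an additional AE assessment is performed 30-45 days from final administration of study treatment". No arm is singled out, so this is the last scheduled AE assessment in Arm B.

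**Arm A only.** Footnote p adds a later contact: "An adverse event assessment is performed 90 days (-15/+30 days) after the last dose of pembrolizumab (Arm A patients only". Section 5.8 has the same contact with a different starting point: "An additional adverse event assessment will be performed 90 days (-15/+30 days) after the last dose of treatment for participants who receive pembrolizumab".

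**Serious events.** Section 7.2 requires reporting to the Sponsor-Investigator "within 30 days of the last dose of treatment on the local institutional SAE form (90 days for pembrolizumab". Section 7.6, limited to Arm A, runs "through 90 days following cessation of pembrolizumab, or the initiation of new anti-cancer therapy, whichever is earlier", whether or not the event is related, and leaves out deaths from progression of the cancer under study. Section 7.7 is not limited to one arm: "All SAEs from the time the subject signs the informed consent and until 30 days after the last dose of study drug must be reported". It also covers later events: "Any SAE that occurs 30 days after the last dose of study drug and is assessed as possibly related to study drug must be reported".

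**Analysis.** Section 13.6 makes patients evaluable for toxicity from their first treatment and states: "The incidence rates of any grade 3 or higher toxicity will be compared across arms", by a two-sided Fisher's exact test. Neither Section 13.6 nor the safety population in Section 13.8.2 gives an end date, a treatment-emergent definition or an adjustment for length of observation. No alpha is stated for this test.

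**The concern.** A crude proportion of patients with at least one Grade 3+ event can only grow as observation lengthens. If one arm is asked about events for longer, its proportion can be higher even when the drugs are equally toxic. The extra period follows the end of treatment, when progression and next-line therapy also produce Grade 3+ events. Routine reporting in Section 7.8 covers Grade 2 and above with no attribution filter, so such events would enter the Arm A count. In Arm B no scheduled contact looks for them.

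Comparative safety is a stated secondary objective (Section 1.3), and the Fisher test is the only between-arm toxicity test in Section 13.6. The risk is that part of an apparent excess on the combination reflects how long patients were asked.

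**Working it through.** The plan gives no rate, difference, power or alpha for this comparison, so there is no figure to reproduce. The check has two parts.

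**1. Length of the gap**

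- Last assessment common to both arms: day 30-45 (footnote m).
- Extra Arm A assessment: 90 - 15 = day 75 to 90 + 30 = day 120 (footnote p).
- The extra period therefore lasts between 75 - 45 = 30 days and 120 - 30 = 90 days. From day 45 to the nominal day 90 it is 45 days.
- It can be shorter still. Footnote p counts from the last pembrolizumab dose, and Section 6.1.1 lets either drug stop while the other continues. If pembrolizumab stops well before sacituzumab govitecan, the contact may fall during treatment and add nothing.

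**2. Illustration of size**

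Inputs:

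- 55 patients per arm: target enrolment, Section 13.1.
- Base rate pB of 75%: approximate Grade 3+ AE rate on sacituzumab govitecan in Section 7.1.2, from a population of mixed tumours and doses. A 60% rate is an assumed alternative.
- Alpha of 0.05, two-sided: assumed.
- f, the share of patients still free of a Grade 3+ event who have a first one in the extra period: assumed.

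True toxicity is equal, so Arm A differs only through the extra period:

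pA = pB + (1 - pB) x f

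For example, with pB = 75% and f = 20%, pA = 0.75 + 0.25 x 0.20 = 80%. The rejection probability comes from exact enumeration of all 55-versus-55 Fisher tables.

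| pB | f | pA | Artificial excess (points) | Fisher rejection |
|---|---|---|---|---|
| 75% | 0 | 75% | 0 | 3.0% |
| 75% | 5% | 76.25% | 1.25 | 3.1% |
| 75% | 10% | 77.5% | 2.5 | 3.7% |
| 75% | 20% | 80% | 5.0 | 6.1% |
| 75% | 30% | 82.5% | 7.5 | 10.8% |
| 60% | 0 | 60% | 0 | 3.0% |
| 60% | 5% | 62% | 2.0 | 3.4% |
| 60% | 10% | 64% | 4.0 | 4.7% |
| 60% | 20% | 68% | 8.0 | 10.2% |
| 60% | 30% | 72% | 12.0 | 20.7% |

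The rise is in one direction. At 75% and f = 30%, 10.7 of the 10.8 points are rejections with Arm A worse.

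**How large might f be?** Section 7.1.2 gives a mean treatment duration of 160 days. Treat 75% over 160 + 30 = 190 days as a constant hazard: h = -ln(0.25)/190 = 0.0073 per day. Over the 45 days from day 45 to day 90:

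- All of that hazard persists: f = 1 - exp(-0.0073 x 45) = 28%, rejection 9.7%.
- Half persists: f = 15%, rejection 4.7%.
- A quarter persists: f = 8%, rejection 3.4%.

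Turned round, f = 20% needs -ln(0.80)/(0.0073 x 45) = 68% of the on-treatment hazard to continue off drug, and f = 30% needs 109%. Across gap lengths, the shortest (30 days) with a quarter of the hazard gives 3.2%. The longest (90 days) with all of it gives 27.3%. The second is an outer bound, not an expectation.

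**The case against.** Much of the case on the other side stands.

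- **Late events can be drug effects.** Section 6.2 says immune-related events may appear months after the last pembrolizumab dose, and Section 2.3.3 gives a half-life of about 4 weeks. A reader might infer that any extra Grade 3+ events in Arm A come from observation time and not from the drug. The documents do not support that. Some would be genuine pembrolizumab toxicity, and this is a sound reason for the longer collection.
- **The gap is not a uniform 60 days.** A reader might infer that everything from day 31 to day 90 is counted in Arm A alone. Footnote m contradicts this, since both arms are assessed at 30-45 days.
- **Some late events are balanced or cut off.** Section 7.7 takes in possibly related serious events after 30 days in either arm. Section 7.6 stops Arm A serious-event reporting at new anti-cancer therapy. Section 5.8 follows AEs that led to removal from therapy until resolution or stabilization in both arms. These provisions are partial: footnote p has no stop at new therapy, and non-serious or unrelated Grade 3+ events are not evened out.
- **Only first events matter.** With a high base rate, few patients remain who could add to the difference. At f of 5-10% the illustrated rejection probability stays below 5%.
- **A 30-day cut leans the other way.** It leaves late immune events out of the main test. The fix must answer this openly.

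Toxicity might also be read as treatment-related only, which would remove background events. Section 13.6 does not say so, and in an open-label trial attribution would be made with the arm known.

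**Conclusion.** The unequal follow-up is explicit, and nothing in Section 13.6 or 13.8.2 evens it out. As written, late events unrelated to pembrolizumab are systematically collected in Arm A only: those from progression and, through footnote p, from next-line therapy. The direction is therefore known: against Arm A.

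The size is not known. The table depends on assumed values of f and alpha, an assumed 60% or borrowed 75% base rate, and full target enrolment. The effect is negligible at f of 5-10% and appreciable at 20-30%, which on the constant-hazard sketch at a 75% base rate needs about two thirds or more of the on-treatment hazard to persist. A reader might take the higher figures as the trial's false-positive rate for toxicity; the documents give no basis for that.

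Severity is low to moderate. This is a secondary safety comparison with no stated alpha or decision rule, and Section 13.6 also reports toxicity by grade and arm with confidence intervals. The fault lies in the missing analysis window, not in the 90-day collection.

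**What to change.** In Section 13.6, state that the between-arm Grade 3+ test and the side-by-side toxicity tables use one window in both arms: first dose to 30 days after the last dose of any study drug, cut at the start of new anti-cancer therapy. Both arms are already assessed to that point, and Section 5.6.1 already records therapy to 30 days after the last dose. With a common window, equal toxicity gives about 3.0% rejection at a 75% base rate.

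Report later Arm A events, including immune-related ones, separately and descriptively. Add a comparison of all collected events as a labelled sensitivity analysis, and state the alpha for the test.

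Keep the 90-day collection. Reconcile its two starting points: the last dose of treatment in Section 5.8 and the last dose of pembrolizumab in footnote p.

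The cost is a short addition to Section 13.6, one listing and one sensitivity table, with no new visits. The downside is that late immune-related events are described and not part of the main test. Collecting AEs to 90 days in both arms would avoid this, but needs an added Arm B contact.

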11 MEASUREMENT OF EFFECT

For the purposes of this study, participants should be re-evaluated for response every 9 weeks. If treatment is delayed, scans will also be delayed to align with cycles of treatment received, rather than weeks on study.

11.1 Antitumor Effect – Solid tumors

Response and progression in sites of metastases will be evaluated in this study using the international criteria proposed by the RECIST 1.1 criteria⁹⁷. Changes in the largest diameter (unidimensional measurement) of the tumor lesions and the shortest diameter in the case of malignant lymph nodes are used in the RECIST criteria.

For any subject who shows first radiologic evidence of progressive disease (PD) by RECIST 1.1 and is deemed clinically stable, it is at the discretion of the investigator to continue treating the subject until progression is confirmed at the next scheduled restaging. These cases should be discussed with the Principal Investigator.

- If progression is not confirmed on the subsequent scan, the subject should continue to receive treatment if the treating investigator feels that the participant is clinically stable, demonstrates improved condition, or is clearly continuing to benefit from the treatment. In this case, radiographic scans should continue to be performed according to the study calendar (i.e., every 9 weeks).
- If radiologic progression is confirmed on the subsequent scan, then the subject should be discontinued from all study treatment.

In all participants, the date of progression for the primary endpoint will be documented as the first date progression was observed.

11.1.1 RECIST 1.1 Definitions

Evaluable for Target Disease response. Only those participants who have measurable disease present at baseline, have received at least one cycle of therapy, and have had their disease re-evaluated will be considered evaluable for target disease response. These participants will have their response classified according to the definitions stated below. (Note: Participants who exhibit objective disease progression prior to the end of cycle 1 will also be considered evaluable.)

Evaluable Non-Target Disease Response. Participants who have lesions present at baseline that are evaluable but do not meet the definitions of measurable disease, have received at least one cycle of therapy, and have had their disease re-evaluated will be considered evaluable for non-target disease. The response assessment is based on the presence, absence, or unequivocal progression of the lesions.

